Other international guidelines recommend primary cervical screening with hr-HPV(16), and management protocols differ slightly on the referral pathway to colposcopy, with some recommending partial genotyping and direct referral to colposcopy for women testing positive for the highest risk HPV (16 or 18)(17). In our cohort, there is little evidence to determine the best cervical screening algorithm, so for this reason we have elected to offer colposcopy to all women testing positive for hr-HPV as well as those with abnormal cervical cytology.

The GeneXpert HPV Assay (Cepheid, Sunnydale, California, USA) is a clinically validated real-time polymerase chain reaction (PCR) assay, which uses a single-use cartridge for the detection of 14 types of hr-HPV in 3 channels (HPV 16, HPV 18/45, and other hr-HPV 31/33/35/52/58/51/59/39/56/66/68)(18). The NHS Cervical Screening Programme (NHSCSP) lists the Cepheid GeneXpert as acceptable for use within screening for HPV triage and test of cure(19).

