**Secondary objectives:**

- To identify the prevalence of high-risk HPV by subtype in a cohort of sexually active women with PaHIV aged  $\geq 18$  years
- To identify the prevalence of CIN2+ in a cohort of sexually active women with PaHIV aged  $\geq 18$  years
- Explore the use of HPV testing as a primary screening tool compared with cervical cytology in this cohort
- Characterisation of immunological and other correlates with high-risk HPV carriage, cervical abnormalities and CIN2+
- Investigate antibody titres to the HPV in vaccinated and unvaccinated women and compare this to responses to other vaccinations (e.g. hepatitis B)
- Explore the relationship between HPV-antibody titres and current immune function (CD4 count) and CD4 count at the time of vaccination
- Explore the uptake and acceptability of cervical screening before the age of 25 in this cohort
- Explore the cost-benefit of providing cervical screening before the age of 25 in this cohort

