### 4. STUDY DESIGN

This is an observational study of cervical cytology and hr-HPV carriage in young females attending a large tertiary referral centre providing HIV care for perinatally acquired HIV infection (n=80). Recruitment will be over 18 months from the study start date or until the planned sample size is recruited. Consenting study participants will give consent to access HPV vaccination history from GP records with the dates and vaccines received.

Eligible young women ( $\geq 18$  years with PaHIV infection) will be invited to join the study. They will be given time to read the patient information sheet and written informed consent will be taken by a study team member. Women will be recruited into one of two cohorts: (Cohort 1) Aged  $\geq 18$  and sexually active, (Cohort 2) Aged  $\geq 18$  and not sexually active.

At enrolment, a single study visit will be required for both cohorts, during which, a venous blood draw of 6mls will be taken plus an optional additional 30mls (36mls total) and an optional urine sample for the Biobank. Participants will be asked to complete a short 1-page questionnaire and a data collection sheet will be completed by study staff. Women enrolled into cohort 1 will also have a speculum examination and a cervical sample will be tested for hr-HPV using the Cepheid GeneXpert HPV and sent for cytology in routine NHS laboratories.

Results of cervical cytology and cervical hr-HPV testing will be given to the study participants in cohort 1. This will either be at an arranged second visit, or via a phone consultation, email or letter depending on the preferences of the individual. Referral to colposcopy services will be made in accordance with current national clinical pathways for any young woman with

abnormal cytology results. In the case of normal cytology in the presence of hr-HPV, these women will also be referred for colposcopic examination. The blood HPV serology are for research purposes only and hence individual results will not be given back to the study participants. At the end of the study, aggregate results will be shared with the study participants.

The HPV vaccination is now available to all women in the UK aged less than 25 years. If women have not been vaccinated at the time of enrolment but are subsequently vaccinated, we will consent them for repeat serological testing at the next clinic appointment following the completion of the HPV vaccine course.

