### 5.2 Inclusion criteria

- Cohort 1:
  - PaHIV females age 18 years and older
  - Sexually active
  - Able to give informed consent
- Cohort 2:
  - PaHIV females age 18 years and older
  - Able to give informed consent

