Visit 1 will either be at the time of the screening visit, their next routine clinic visit or as an additional study visit depending on participant preferences.

**6.3 Visit 1:** At visit 1 (either the same day as study enrolment or scheduled to another date as per participant preference) each participant will have their eligibility and consent in the trial confirmed. Clinical and demographic information will be recorded on the study CRF and will include:

- Age
- Ethnicity
- Current CD4 count
- Current CD4:CD8 ratio
- Current HIV-1 RNA viral load
- Nadir CD4 count
- Length of viral suppression <50 copies/ml
- Current antiretroviral therapy
- Concomitant medications
- Smoking
- Menarche
- Coitarche
- Obstetric history
- Gynaecology history including previous smear results
- Contraception
- HPV vaccination history (including age at vaccination, type, number of doses)
- Other vaccination history
- CD4 count at time of first HPV vaccination (if known)
- Lifetime number of sexual partners
- Diagnosed STIs
- History of genital warts
- Consent to access GP records for HPV vaccination details where GP aware of status

[figure not shown]
Investigations:

- Cervical smear test
- Cervical sampling for hr-HPV testing
- Blood for serology
- Optional Blood and urine for Biobank

**6.4 Visit 2 (optional for cohort 1, 2-4 weeks later):** Attendance for results of the cervical cytology and hr-HPV will be made with the research team. If a participant does not wish to attend for a second visit they will be given the option to get their results by phone, letter or email. All other tests are considered research tests and the individual results will not be given back to the study participant. Any abnormal cervical cytology result will be referred to local colposcopy services in accordance with local and British guidelines. Women who test positive for any hr-HPV will also be referred to colposcopy for the purposes of this study. Consent will be sought to collect outcome data following gynaecology referral.

**6.5 Visit 3:** For those women who receive HPV vaccination after enrolment into the study, repeat blood tests will be taken at the next clinic visit after completion of the vaccine course.

The study procedures algorithm can be seen in Figure 1.

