## 9. STATISTICAL ANALYSIS

- **Summarising data:** Characteristics of the study population will be described using mean and standard deviation, median and interquartile range, or number and percentage as appropriate. This information will also be stratified by age group.
- **Primary outcome:** The prevalence of cervical abnormalities within the cohort and by age group (18-24 and  $\geq 25$ ) will be calculated
- **Secondary outcomes:**
  - The prevalence of hr-HPV by type in young women with PaHIV will be calculated and stratified by age group
  - The prevalence of CIN2+ in young women with PaHIV will be calculated and stratified by age group
  - Comparison of HPV positivity with cervical abnormalities in young women with PaHIV
  - Characterisation of immunological and other correlates with hr-HPV carriage, cervical cytology results, CIN2+ and HPV type-specific antibody titres using the appropriate statistical test (Pearson's chi squared, Fisher's exact, Wilcoxon rank sum)
  - A measurement of HPV type-specific antibody titres in HPV vaccinated and unvaccinated young women with PaHIV, and a comparison with e.g. antibody titres to hepatitis B vaccination
  - Correlations of HPV-antibody titres and current immune function (CD4 count) and CD4 count at the time of vaccination
  - Acceptability will be assessed by the proportion of women who are offered enhanced cervical screening but decline.
  - Cost effectiveness will be assessed by evaluating the yield of abnormal results (cytology and hr-HPV) versus the cost of the tests

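### The Section 9 cost item counts only test costs, leaves out colposcopy referrals and CIN2+, and does not name ages 18-24 as the group reported

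*Combined protocol and SAP*

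**What the plan says.** The objective, in Section 3 and in the trial summary, reads: "Explore the cost-benefit of providing cervical screening before the age of 25 in this cohort". The only analysis text for it is the last bullet of Section 9: "Cost effectiveness will be assessed by evaluating the yield of abnormal results (cytology and hr-HPV) versus the cost of the tests".

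Four other parts of the protocol bear on that bullet:

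- **Age.** Section 5.2 admits to Cohort 1 "PaHIV females age 18 years and older", with no upper limit. Section 9 defines two age groups, 18-24 and 25 or over, for the primary outcome, and stratifies hr-HPV and CIN2+ by age group. Section 1 notes that women with HIV already have yearly cytology from age 25.
- **Referral.** Section 2 states: "we have elected to offer colposcopy to all women testing positive for hr-HPV as well as those with abnormal cervical cytology". Section 4 adds: "In the case of normal cytology in the presence of hr-HPV, these women will also be referred for colposcopic examination". Section 6.4 repeats it: "Women who test positive for any hr-HPV will also be referred to colposcopy for the purposes of this study".
- **Disease.** Section 9 plans: "The prevalence of CIN2+ in young women with PaHIV will be calculated and stratified by age group".
- **Outcome data.** Section 6.4 says: "Consent will be sought to collect outcome data following gynaecology referral".

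No section gives a unit cost, an expected hr-HPV prevalence or an expected age split.

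**The concern.** The cost bullet does not match its objective in three respects.

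1. **Cost.** Colposcopy follows directly from a positive result under this protocol, yet the bullet costs the tests alone and no other section costs the referrals.
2. **Yield.** It counts abnormal cytology and hr-HPV results. CIN2+ is closer to the benefit that the rationale in Section 1 argues for, namely earlier detection of pre-cancer, but it is not set beside cost.
3. **Population.** The question is about women under 25, and the bullet does not say that they are the group reported.

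A reader deciding whether to offer screening before 25 would see what the tests cost and how many abnormal results they gave. The reader would not see what those results cost to follow up or how much disease they led to. The name also shifts, from cost-benefit in the objective to cost effectiveness in the analysis. Neither name fits, because benefit is not valued and there is no comparator, such as no screening before 25.

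**Working it through.** The plan states no cost figure, so there is none to reproduce. The mismatch comes from setting the passages side by side. The arithmetic below only illustrates its possible size.

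**Inputs**

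- Cohort 1 size: 50 (Section 1).
- Abnormal cytology c = 0.17 (Section 2, first smears in the clinic's own earlier data).
- hr-HPV positivity h = 0.30, 0.50, 0.70. Assumed.
- r = cost of one colposcopy divided by the cost of both tests for one woman: 0.5, 1, 2, 5. Assumed.

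**Step 1: women referred.** A woman is referred if either result is abnormal. The overlap is unknown, so the referred share U is bounded:

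- full overlap (every abnormal smear is also hr-HPV positive): U = max(c, h) = h
- no overlap: U = c + h

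The share with hr-HPV and normal cytology runs from h − c (full overlap) to h (no overlap). Multiplying by 50:

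| h | U | Referred, of 50 | Of these, hr-HPV with normal cytology |
|---|---|---|---|
| 30% | 0.30-0.47 | 15-23.5 | 6.5-15 |
| 50% | 0.50-0.67 | 25-33.5 | 16.5-25 |
| 70% | 0.70-0.87 | 35-43.5 | 26.5-35 |

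**Step 2: what the omission could amount to.** Total cost relative to test-only cost is 1 + r × U:

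| h | r = 0.5 | r = 1 | r = 2 | r = 5 |
|---|---|---|---|---|
| 30% | 1.15-1.24 | 1.30-1.47 | 1.60-1.94 | 2.50-3.35 |
| 50% | 1.25-1.34 | 1.50-1.67 | 2.00-2.34 | 3.50-4.35 |
| 70% | 1.35-1.44 | 1.70-1.87 | 2.40-2.74 | 4.50-5.35 |

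The range is wide because r is not in the documents.

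**Step 3: why the age group should be stated.** At 17%, one abnormal smear takes 1/0.17 = 5.9 tests at ages 18-24. Suppose 25 of the 50 are under 25 (assumed) and all ages were combined. If the older women had 30% abnormal, the pooled prevalence would be (0.17 + 0.30)/2 = 0.235, or 1/0.235 = 4.3 tests. If they had 10%, it would be 0.135, or 7.4 tests. Both older-group values are assumed. The difference can go either way.

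**Step 4: how much CIN2+ can carry.** With 25 women under 25 (assumed), the chance of no CIN2+ is 0.96^25 = 36% at 4% prevalence and 0.92^25 = 12% at 8%. With 15 women the figures are 54% and 29%; with 35 women, 24% and 5%. The exact 95% upper limit for 0 of 25 is 13.7%. CIN2+ belongs beside the cost as a count with its interval, but not as the main denominator.

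**The case against.** The strongest reply has four parts.

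- **The data are already planned.** Abnormal cytology, hr-HPV and CIN2+ are all reported by age group, and the objective is itself limited to women under 25. This stands in part. A reader might infer that the cost figure will be pooled over ages, or that the study does not report CIN2+. The documents do not support either: the bullet is silent on age, and CIN2+ is a separate outcome. What remains is that the plan does not commit to an under-25 cost figure, and no planned output supplies a colposcopy cost.
- **Test-only costing has a rationale.** Referral of hr-HPV-positive women with normal cytology is made for this study, because the best algorithm is unknown (Section 2). The same section describes cytology triage of hr-HPV-positive women in the planned national programme. Charging every study referral to screening could overstate what providing it would cost. This stands, and the fix must show those referrals separately in both number and cost.
- **Higher hr-HPV positivity need not make the planned measure misleading.** A reader might infer that the measure flatters screening as hr-HPV positivity rises, with no more disease found, while true cost moves in the opposite direction. The documents do not support this. Section 9 defines no ratio and does not say that the two yields are summed. Holding CIN2+ fixed would be the reader's assumption. On a like-for-like ratio that includes colposcopy, (1 + rU)/(c + h), cost per abnormal result also falls from h = 30% to 70%: at r = 0.5 from 1.235/0.47 = 2.63 to 1.435/0.87 = 1.65 (37%, no overlap), and at r = 5 from 2.50/0.47 = 5.32 to 4.50/0.87 = 5.17 (3%, full overlap).
- **This is an exploratory item with no decision attached.** Agreed, and it sets the severity.

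**Conclusion.** The point holds as a minor mismatch between objective and analysis. Followed as written, the bullet leaves out a direct consequence of the screening it costs and does not relate cost to the disease endpoint. It also leaves the reported age group unstated. These three statements rest on the text alone.

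The size rests on assumptions. At hr-HPV positivity of 30% to 70% and 17% abnormal cytology, between 15 and 43.5 of 50 women would be referred without being costed. Between 6.5 and 35 of them would be referred on hr-HPV with normal cytology. The cost cannot be fixed without a unit cost.

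The direction in which the planned figure would mislead is not established. The primary outcome and the other secondary outcomes are unaffected.

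**What to change.** Replace the cost bullet in Section 9 with text to this effect:

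> For Cohort 1 women aged 18-24 (all ages secondary) we will report: (a) test cost and number of abnormal results, separately for cytology and hr-HPV; (b) the number of resulting colposcopy referrals and their cost at a stated unit cost, with number and cost shown separately for women referred on hr-HPV with normal cytology; (c) total cost with and without those separately shown referrals; (d) beside these, the number with CIN2+, the number of women with outcome data as its denominator, and an exact binomial 95% interval. Cost per CIN2+ is descriptive only and will not be calculated if no CIN2+ is found. This is an exploratory cost-and-yield description, not a cost-benefit analysis.

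Reword the objective in Sections 1 and 3 to match the last sentence.

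The price is one colposcopy unit cost and possibly one CRF field for referral and attendance, which is not among the items listed in Section 6.3. No extra participants, visits or samples are needed. Outcome data depend on consent, so some CIN2+ status may be missing, and the denominator must show this. The resulting figure will be less favourable than a test-only one, and imprecise. The change takes no position on which referral rule should apply.

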## 10. DATA MANAGEMENT

### 10.1 Access to data

Direct access will be granted to authorised representatives from the Sponsor or host institution for monitoring and/or audit of the study to ensure compliance with UK GCP and GDPR regulations.

### 10.2 Data recording and record keeping

#### a) CRF

The demographic and clinical data will be collected in the study CRF. Any relevant hard copies of source data will be filed locally under patients' unique identifier in accordance with Data Protection Act agreed practice. In all locations, any hard copy patient data will be stored in locked, filing cabinets with access restricted to pre-specified essential users.

#### b) Confidentiality

Information related to participants should be kept confidential and managed in accordance with the Data Protection Act, NHS Caldecott Principles, The Research Governance Framework for Health and Social Care, and the conditions of Research Ethics Committee Approval.

#### c) Record Retention and Archiving

The investigator will retain essential documents for 10 years as per Imperial College London policy (the sponsor). This includes subject files and other source data (including copies of protocols, CRFs, original reports of test results, correspondence, records of informed consent, and other documents pertaining to the conduct of the study). Documents will be stored in such a way that they can be accessed/data retrieved at a later date. Consideration will be given to security and environmental risks.

No study document will be destroyed without prior written agreement between the Sponsor and the investigator. Should the investigator wish to assign the study records to another party or move them to another location, written agreement must be obtained from the Sponsor.

## 11. QUALITY ASSURANCE PROCEDURES

The study may be monitored, by the study sponsor, or audited in accordance with the current approved protocol, ICH GCP, relevant regulations and standard operating procedures.

## 12. ADVERSE EVENTS

### 12.1 Definitions

(a) Adverse Event (AE): any untoward medical occurrence in a patient or clinical study subject.

(b) Serious Adverse Event (SAE): any untoward and unexpected medical occurrence or effect that:

- Results in death
- Is life-threatening – *refers to an event in which the subject was at risk of death at the time of the event; it does not refer to an event which hypothetically might have caused death if it were more severe*
- Requires hospitalisation
- Results in persistent or significant disability or incapacity
- Is a congenital anomaly or birth defect

Medical judgement should be exercised in deciding whether an AE is serious in other situations. Important AEs that are not immediately life-threatening or do not result in death or hospitalisation but may jeopardise the subject or may require intervention to prevent one of the other outcomes listed in the definition above, should also be considered serious.

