**Figure 1: Management protocol for participants**

## 7. STUDY PROCEDURES

### 7.1 Cervical sampling for smear test and hr-HPV testing

Cervical cytology will be performed by a trained healthcare professional in accordance with current guidance in England for liquid based cytology using a disposable plastic speculum for speculum examination. A 1ml aliquot will be analysed for hr-HPV using the Cepheid GeneXpert HPV.

The risks to the participant of the procedure are discomfort and vaginal bleeding after the procedure. The participant may also feel discomfort vaginally following the speculum examination.

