#### (b) Serious AEs

A SAE form should be completed and sent to the Chief Investigator within 24 hours.

All SAEs should be reported to the Research Ethics Committee where in the opinion of the Chief Investigator, the event was:

- 'related', i.e. resulted from the administration of any of the research procedures; and
- 'unexpected', i.e. an event that is not listed in the protocol as an expected occurrence

Reports of related and unexpected SAEs should be submitted within 15 days of the Chief Investigator becoming aware of the event. The Chief Investigator must also notify the Sponsor of all SAEs.

Local investigators should report any SAEs as required by their Local Research Ethics Committee, Sponsor and/or Research & Development Office.

Contact details for reporting SAEs:

[[contact]](mailto:[contact])

Chief Investigator email [name], [[contact]](mailto:[contact])

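### Section 12.1(b) makes 'unexpected' part of the SAE definition, which conflicts with 12.2(b) and may keep serious but expected events out of 24-hour and Sponsor reporting

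*Combined protocol and SAP*

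**What the plan says.** Section 12.1(a) defines an AE as "any untoward medical occurrence in a patient or clinical study subject", with no condition on expectedness. Section 12.1(b) adds one for SAEs: an SAE is "any untoward and unexpected medical occurrence or effect that" leads to one of five outcomes, among them "Requires hospitalisation". A paragraph after the list allows discretion: "Medical judgement should be exercised in deciding whether an AE is serious in other situations".

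Section 12.2 opens with a general duty to report every AE, but gives no deadline and no Sponsor step at that point. Section 12.2(a) asks that non-serious AEs be recorded, expected or not. Section 12.2(b) attaches specific duties to SAE status. One is a deadline: "A SAE form should be completed and sent to the Chief Investigator within 24 hours". Another is onward notice: "The Chief Investigator must also notify the Sponsor of all SAEs". SAEs go to the REC only if they are both related and unexpected, the latter explained as "unexpected', i.e. an event that is not listed in the protocol as an expected occurrence".

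The protocol names several procedure risks. Section 7.1 says of cervical sampling: "The risks to the participant of the procedure are discomfort and vaginal bleeding after the procedure". Section 7.2 names faintness from a vasovagal response or hypotension at venepuncture, and section 19 adds syncope.

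**The concern.** Seriousness and expectedness are separate attributes of an event. Seriousness describes the outcome; expectedness asks whether the protocol foresaw the event. Section 12.1(b) merges them, and 12.2(b) then treats them as separate.

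This matters because the 24-hour form and the Sponsor notice depend on SAE status alone. If an event is serious but judged expected, a reader who follows 12.1(b) to the letter could decide that neither step applies. The events open to that decision include the harms that the protocol itself attributes to its procedures. Participants come from two clinics (section 5.1). One could apply the literal definition and the other the evident intent of 12.2(b), so that similar events would be reported differently.

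**Working it through.** No arithmetic applies. The check sets the definition beside the reporting rules.

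**Inputs.** Let S be the events with a listed serious outcome (12.1(b)), U the events not listed in the protocol as expected (12.2(b)), and R the events related to a research procedure (12.2(b)). The discretionary paragraph is taken up at the end.

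| Step | As written | With 'and unexpected' deleted from 12.1(b) |
|---|---|---|
| Counts as an SAE | S and U | S |
| 24-hour form to the Chief Investigator | S and U | S |
| Notice to the Sponsor | S and U | S |
| Report to the REC | (S and U) and R and U = S and R and U | S and R and U |

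**What the table shows.**

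1. In the REC row as written, U appears twice and the second U removes nothing. Section 12.2(b) nevertheless states it as a separate condition and refers to SAEs that are both related and unexpected. That makes sense only if an SAE can be expected. Section 12.2(a) likewise treats expectedness as separate from seriousness.
2. The two columns differ only for events that are serious and not U. Those events gain the 24-hour form and the Sponsor notice. Local investigators' onward SAE reporting, also in 12.2(b), changes in the same way.
3. The REC row is the same in both columns, so the deletion changes nothing there.
4. Serious events that the protocol does not list as expected are SAEs under either wording.

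**An example.** Take an admission for bleeding after the smear. The admission meets a listed outcome, so the event is in S. Whether it is in U depends on whether naming bleeding as a risk in 7.1 amounts to listing it as an expected occurrence. If it does, the event fails the opening words of 12.1(b) and the two steps are not triggered. If it does not, the event is an SAE as written.

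**Whether the discretionary paragraph closes the gap.** It speaks of situations other than those listed, and goes on to important AEs that fall short of death or admission. It does not mention expectedness. Read strictly, a listed faint without admission could be judged serious, while the same faint with admission would fail the main definition. The paragraph leaves some room for judgement but does not reliably cover this case.

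**Size.** The documents give no rate of serious procedure-related events, so no expected count can be calculated. The planned exposure is 50 women having cervical sampling and 80 having blood taken, with repeat blood only for those vaccinated after enrolment.

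**The case against.** The strongest reply is that the harm depends on an inference. The protocol has no list headed as expected events. Sections 7.1, 7.2 and 19 speak of risks and side effects, mostly minor ones, and none mentions bleeding or syncope severe enough for admission. An investigator could fairly call such an admission unexpected in severity and report it as an SAE under the present wording. This stands, and it is why the consequence is put as 'may' and not 'will'.

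A reader might go further and infer that listed harms can never become SAEs, that they drop into 12.2(a), or that they escape safety oversight. The documents do not support any of these:

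- The judgement paragraph leaves an investigator some discretion.
- Section 12.2(a) covers non-serious AEs, so an admission does not clearly belong there. At most it falls between the two categories.
- Section 12.2 requires all AEs to be reported and directs questions to the Chief Investigator. What is at risk is the 24-hour form and the explicit Sponsor notice, not reporting as such.
- Events judged expected would not go to the REC even after the correction.

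It can also be said that section 12, read as a whole, shows the authors meant SAEs to include expected events. That is probably right. It supports correcting 12.1(b), because staff should not have to infer the rule from a redundancy elsewhere.

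**Conclusion.** The point holds as an internal conflict with a possible safety-reporting consequence. The conflict itself needs no assumption: 12.1(b) requires every SAE to be unexpected, and 12.2(b) tests for it again. The consequence rests on two assumptions: that a named risk is treated as an expected occurrence whatever its severity, and that staff apply 12.1(b) literally. Where both hold, a serious event of that kind may miss the 24-hour form and the Sponsor notice.

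It would be tempting to say that the reported rate of expected SAEs is zero by definition. That takes both assumptions as settled, and the documents settle neither. The number of events affected is likely to be small in a low-risk observational study of 80 women. No objective in section 3 and no analysis in section 9 uses an SAE count, so the prevalence estimates are unaffected.

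**What to change.** Delete 'and unexpected' from the opening words of 12.1(b), so that an SAE is defined by its outcome alone. Leave 12.2(b) as it stands, with 'related' and 'unexpected' serving only as the criteria for reporting to the REC. Every sentence in section 12 then has a function.

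The cost is two words in an amendment and at most a few extra SAE forms and Sponsor notices. Sample size, procedures, analyses and REC reporting do not change.
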